6.3.4 Study Intervention Modifications

If at interim analyses, an effect size of $d = 0.25$ or greater reflecting improvements from piano training relative to controls is not observed on at least one of the cognitive outcomes measures (verbal fluency, Trails, Digit Coding) relative to controls, we will randomize the remaining participants to 25 sessions (i.e., 37.5 hours) instead of 20 sessions (i.e., 30 hours) of training.

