 - **Verbal Fluency**¹⁰⁹. Executive function will be assessed with phonemic, category, and category switching verbal fluency tasks. Phonemic fluency consists of three, one-minute trials during which the examinee names as many words as can be thought of that begin with a given letter, excluding proper nouns, numbers, and the same word with a different suffix will also be assessed (test-retest reliability=.88)¹¹⁰. Category fluency is designed to measure the speed and flexibility of verbal thought processes ($r=0.82$; sensitivity=.88; specificity=.96)^{109, 111}. A switching condition is included that requires participants to alternate between sets (e.g. naming fruits and furniture) ($r=0.51$). Different versions of this measure will be administered at baseline and post-test. The BHR, Clothes/Girls' Names, and Vegetables/Musical Instruments will be administered at baseline while the FAS, Animals/Boys' Names, and Fruits/Furniture version will be administered at post-test. The recorded score is the number of correct items for each task.
 - **Trail Making Test Part A**. Speed of processing is evaluated using the Trail Making Test Part A. This test ($r=.53-.64$), requires participants to draw a line connecting a series of numbers in sequential order (1-2-3, etc)¹¹². The recorded score is the time required to complete the task¹¹³.
 - **Trail Making Test Part B**. Executive function is evaluated using the Trail Making Test Part B, which is a reliable measure ($r=.54-.62$) that requires participants to draw a line connecting a series of number and letters in alternating, sequential order (1-A-2-B, etc) (Strauss et al., 2006). The recorded score is the time required to complete the task^{113, 114}.
 - **Digit Symbol Coding**. Cognitive speed of processing is evaluated using Digit Symbol Coding¹⁰⁹. This test consists of 135 blank squares that are paired with a number from one to nine. A reference key links each number to a different geometric figure. Using the reference key, participants have 120 seconds to copy the geometric figure assigned to the number into the blank boxes. Scaled scores are obtained by subtracting the number of errors from the number of correct responses. Lower scores indicate better performance. Psychometric properties are reported in the manual.
- Outcomes of everyday function include the Timed IADL and TEA tests

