 - **Timed IADL** involves timed performance of five tasks encountered in daily life. The previously validated tasks¹¹⁵ utilize real-world stimuli and represent five IADL domains, including communication (finding a telephone number in a phone book), finance (making change), cooking (reading the first three ingredients on a can of food), shopping (finding two items on a shelf of packaged foods) and medication management (reading the directions on a medicine bottle label). Scores are generated by combining the completion time and error code for each task per standard procedure. Task scores are combined into a single composite by taking the average of z scores computed for each of the five tasks after error correction. Test-retest reliability of the Timed IADL is $r = .85$ ¹¹⁵.
 - **The Test of Everyday Attention (TEA)**^{116, 117} consists of eight sub-tests designed to measure different types of attention. The subtests are designed to mimic everyday tasks that encompass both visual and auditory domains. The test-retest reliability of versions A to B range from .59-.86¹¹⁶. Four of the eight subtests will be administered in this study and include:
 - **Visual Elevator**. Participants count up and down floors as they follow a series of visually presented doors and arrows. An accuracy (how many final floor numbers the participant gets correct out of 10) and timing scores (total time taken for the correct items) are

- obtained. The reported score is the total time taken divided by the number of switches for the correct items and the scaled score. This subtest measures attentional switching¹¹⁷.
- **Elevator Counting with Reversal.** As with the Visual Elevator subtest, participants count up and down as they follow a series of visually presented doors. In this subtest however, the tones are at a fixed speed. The recorded score is the number of correct answers out of 10 and the scaled score. This subtest measures auditory-verbal working memory¹¹⁷.
 - **Telephone Search.** Participants search for symbols while searching for entries on a replicated page of a telephone directory. The recorded score is the time per target score (number of correctly detected symbols divided by the time taken to identify the correctly detected symbols) and the scaled score. This subtest measures selective attention¹¹⁷.

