9.5 Interim Data Analyses

Interim analyses will be conducted in June of 2019, after the pilot, first, and second replicates are completed. We expect that 140 participants will have completed post-test at this time. The purpose will be to confirm feasibility of the training conditions, to assess effect size on cognitive measures from pre- to post- training and adapt number of sessions, if warranted, and to monitor safety.

Interim analyses will be conducted to ensure the safety of the trial. Per NIA, this project does not meet the criteria for requiring a formal Data and Safety Monitoring Plan or Data Safety Monitoring Board because it is not a Phase III clinical trial as defined by NIH. As a behavioral intervention study, this is a phase II efficacy trial¹. At interim analysis, [name] will compare the number of adverse events between the two randomized conditions to assess safety. The two groups will also be compared on attrition rates. Any significant differences between the two conditions in adverse events or attrition rates will be further investigated by [name]. If there is a significant imbalance, confirmed, then [name] will report the findings to the Clinical Trial Coordinator, [name], who is unblinded. The Clinical Trial Coordinator will work with the IRB to decide if the study should be terminated early.

Interim analyses will be conducted to ensure the feasibility of study intervention adherence. If at interim analyses, less than 75% of participants randomized to an arm complete at least 16 sessions (80% of prescribed 20), the intervention arm will be deemed not feasible. If this occurred for both arms, the study will end.

Finally, interim analyses will examine the potential efficacy of the piano training arm. Effect sizes and confidence intervals for all cognitive outcomes will be calculated for pre- to post- training relative to controls. We expect that the piano training arm will produce an improvement of at least $d=0.25$ from baseline to post-test on at least one of the cognitive measures of verbal fluency (phonemic, category or switching), Trails A or B, or Digit Coding, relative to active controls. If an effect size from pre- to post- training relative to controls of this

magnitude is not observed on at least one of these outcomes, we will adapt study procedures by changing the number of training sessions from 20 to 25. In this instance number of training sessions completed will be examined as a covariate in final analyses.

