9.6 Final Data Analyses

Dealing with Score Distribution. We will inspect the distribution of scores to confirm that parametric statistical testing is appropriate. In the event that distributional properties do not support parametric tests, we will compare the results from conventional parametric analyses with (a) results from similar nonparametric testing (e.g., Wilcoxon signed ranks test), (b) results from parametric analyses conducted after the non-normally distributed variables are transformed to improve normality to compare the results with the conventional parametric analyses, and (c) Any illegal values or outliers of $\geq \pm 3z$ will be checked for accuracy with the raw data.

Composite Outcomes. Data reduction in the form of principal component factor analysis (PCA) will be used to derive composite outcomes of CAP, cognition, and everyday function for analyses to reduce the number of comparisons. Baseline data across CAP, cognitive, and everyday function outcomes will be factor analyzed using pairwise deletions. Based on the number of factors derived and factor loadings of the individual measures (.4 or greater), outcome composite scores will be calculated after transforming the baseline data to z scores while taking into account the directional scaling of the items. Post-test scores will be standardized based upon the baseline mean and SD. The baseline factors and loadings will be applied to calculate post-test composite scores.

Preliminary/Descriptive Analyses. Prior to the analyses described below, we will conduct one-way ANOVA or Chi-square analyses as appropriate comparing the randomized groups at baseline on age, race, education, sex, MoCA, GDS, hearing and vision, to ensure that the study randomization procedures were successful. We will also confirm the equivalence of the two randomized conditions by comparing the NICT questionnaire responses. The total across the six items relevant to cognition will be calculated and examined in analyses. If even a marginally significant ($p < .1$) difference is observed for any of these study variables, the pertinent variables will be included as covariates in subsequent analyses.

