Specific Aim 2: To examine the moderating effects of MCI on intervention efficacy. We will also test for moderation effects to determine at what stage along the cognitive status continuum—without MCI vs. MCI—intervention is most effective. To do so, we will examine three-way interactions (MCI x training group x time) for the CAP, cognitive, and everyday function composites. When an interaction is significant, we will stratify analyses by MCI status and examine effect sizes. Effect sizes from pre- to post- training relative to controls will be compared for participants with/without MCI. An alpha of .05 will be used for these analyses.

Participants who score 26 or higher on the MoCA will be defined as no MCI (i.e., cognitively normal). Those participants who score a 20-25 on the MoCA will be defined as MCI if they score a 0.5 on the CDR and have performance at or 1 SD below their age, sex, and education norms on any of the following measures: Trails, Verbal Fluency, Digit Coding, Craft Story Recall, Multilingual Naming Test, or Benson Complex Figure. Those with MoCA scores 20-25 who score 0 on the CDR, but have performance at or 1SD below expected for age, sex, and education will be adjudicated prior to analyses. If an individual scores 20-25 on the MoCA, and 0.5 on the CDR, but has performance above expected on all of the aforementioned measures, their case will be adjudicated prior to analyses. The study physicians will adjudicate such cases prior to coding of MCI status for final analyses.

To quantify the effects of piano training further, in addition to examining composite outcomes as detailed above, we will calculate and report effect sizes for pre-to-post change of piano training relative to controls for each individual measure of CAP, cognition, and everyday function for the sample overall as well as stratified by MCI status and among those who were adherent only (80% or more of sessions completed).

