The randomized groups did not differ in sex, $\chi^2(1)=.787, p=.375$, ethnicity $\chi^2(1)=.167, p=.683$, or race, $\chi^2(1)=.045, p=.832$. The Music Reading Assessment scores did not differ between the two groups, $t(266)=-.958, p=.338$. The randomized groups did not significantly differ in age, $F(1,266)=.293, p=.589$, education, $F(1,266)=.369, p=.544$, MoCA, $F(1,266)=.427, p=.514$, or GDS, $F(1,266)=.943, p=.332$. However, there were marginally significant group differences for PTA in the left ear, $F(1,266)=3.31, p=.070$ and statistically significant group differences for both PTA in the right ear, $F(1,266)=6.69, p=.010$, and visual acuity, $F(1,266)=8.99, p=.003$. The music listening group tended to have worse hearing, while the piano training group tended to have worse visual acuity. See Table 1. The groups also differed significantly in their expectations regarding potential benefits of their randomized group, $F(1,214)=15.07, p<.001$. The piano training group had an average rating of 5.55 while the music listening group had an average rating of 4.99, indicating the piano training condition had higher expectations about the potential effects of their randomized condition. The piano training group also rated their condition as more challenging with 92% agreeing that the intervention was challenging as compared to 86.3% of the music listening group indicating their condition was challenging ($p<.001$).

Principal component analysis with varimax rotation was conducted to reduce the number of variables for analyses. Please see Supplemental Table A for details. The first factor reflected cognitive performance speed and included the Trail Making Test, Digit Coding, and the TEA visual elevator and phone search subtests. The second factor included all three verbal fluency subtests. The third factor reflected CAP and included DDT, DSI, TCS, and WIN. The fourth factor included two indices from the TEA phone search while counting and visual elevator accuracy. The fifth composite included ATTR across- and within- channel performance. Baseline composites of cognitive performance, verbal fluency, ATTR, CAP, and everyday function were created by averaging z scores after the reverse-scaling of items with negative factor loadings. Post-test scores were standardized

by baseline means and *SDs*. Timed IADL performance did not significantly load on any factor and was thus examined separately.

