In the primary analyses, we examined whether performance changed differentially by random assignment across composite outcomes from baseline to post-test as indicated by a significant group-by-time interaction. Covariates included hearing PTA, visual acuity, and expectations. The group-by-time interactions were not statistically significant for any of the outcomes ($ps > .194$). See Table 2. The results did not change when we included only those who were adherent ($ps > .180$). See Supplementary Table B. Piano training did not significantly enhance CAP, cognition, or everyday function as compared to music listening. We further examined if intervention effects varied by MCI status (Supplementary Table B). There were no significant group-by-time-by-MCI status interactions indicating those with and without MCI did not show differential benefit ($ps > .245$). Thus, MCI did not significantly moderate the effects of piano training.

Effect sizes for piano training as compared to music listening are shown in Table 3. Improvements were not evident in the primary analyses, adherent analyses, or the subsample without MCI on measures of CAP, cognition, or everyday function. Participants with MCI randomized to piano training showed potential small effect sizes for improvement relative to music listening on Trails A, Digit Symbol Coding, and one subtest of the TEA ($ds \geq 0.25$). Raincloud plots of individual assessment and composite variables are included in the supplemental materials.

Results indicated significant effects of time for ATTR in all models and significant effects of time for CAP in the primary and adherent analyses indicating improved performance from pre- to post- training. Significant effects of time were found for cognition and TEA in the primary and adherent analyses, indicating a tendency for decline across time. With respect to covariate effects, CAP, ATTR, and cognitive performance were significantly impacted by hearing. Similarly, Timed IADL and cognitive performance varied significantly by visual acuity. Those with poorer hearing or vision tended to perform worse on these outcomes. Interestingly,

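### Section 6.3.5 gives Digit Symbol Coding a direction that contradicts its own formula, and gives Telephone Search a label and formula that are reciprocals; wrong as written, with minor consequence.

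*Combined protocol and SAP*

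**What the plan says.** Section 6.3.5 describes Digit Symbol Coding as 135 squares to be filled in 120 seconds, and then: "Scaled scores are obtained by subtracting the number of errors from the number of correct responses. Lower scores indicate better performance". For the Telephone Search subtest of the Test of Everyday Attention (TEA), the recorded score is the "time per target score (number of correctly detected symbols divided by the time taken to identify the correctly detected symbols"), together with a scaled score.

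The plan uses item direction in three places:

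- **Composites (Section 9.6).** Scores are formed from z scores "taking into account the directional scaling of the items". No direction is listed for any item.
- **Interim rule (Sections 6.3.4 and 9.5).** The number of sessions changes if an effect of 0.25 "is not observed on at least one of the cognitive outcomes measures (verbal fluency, Trails, Digit Coding) relative to controls". Section 9.5 gives the list in full: "at least one of the cognitive measures of verbal fluency (phonemic, category or switching), Trails A or B, or Digit Coding". Digit Coding is therefore one of six scores read singly.
- **Item-level reporting (Section 9.6, Specific Aim 2).** "we will calculate and report effect sizes for pre-to-post change of piano training relative to controls for each individual measure".

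Section 14 (Results) reports that composites were "created by averaging z scores after the reverse-scaling of items with negative factor loadings". The note to Table 14.3 says that d was signed so that a positive value means improvement. The modification log in Section 11.5 touches neither scoring sentence.

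**The concern.** For Digit Coding, the only direction that the documents state for the raw score is opposite to the formula beside it. For Telephone Search, label and formula run in opposite directions, and the choice is more than a sign: a reciprocal also changes the distribution, the z scores and the size of d.

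Cognition is the primary outcome of interest, and Digit Coding is one of its six planned scores. Reversal by factor loading can orient a composite correctly whatever Section 6.3.5 says, but it does nothing for a measure read alone. An analyst who followed the Digit Coding sentence would count a benefit as a harm in the interim rule and in the item-level effect sizes. One reported statement rests on that sign: participants with MCI in the piano arm "showed potential small effect sizes for improvement relative to music listening on Trails A, Digit Symbol Coding, and one subtest of the TEA".

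**Working it through.** **1. Direction implied by each formula (illustrative values).**

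Digit Coding, correct minus errors: 135 − 0 = 135; 70 − 0 = 70; 70 − 5 = 65; 0 − 0 = 0. The score rises with correct responses and falls with errors. Read as lower-is-better, a participant with nothing correct would outrank a perfect one.

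Telephone Search:

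| Targets, seconds | Label: time/targets | Formula: targets/time |
|---|---|---|
| 20 in 50 s | 2.5 | 0.40 |
| 20 in 80 s | 4.0 | 0.25 |
| 10 in 60 s | 6.0 | 0.167 |

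The product of the two is 1 in each row. Better performance lowers the label's score and raises the formula's.

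**2. Effect on the interim rule if Digit Coding were reversed.**

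Inputs from Section 9.5: 140 participants expected, so about 70 per arm; threshold d = 0.25; six scores. Assumed: test-retest correlation r of 0.6 to 0.9, equal correlation ρ of 0 to 0.7 between the six estimates, and normal estimates.

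SE(d) = √[(2/70) × 2(1 − r)], which is 0.151 at r = 0.6 and 0.076 at r = 0.9.

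Chance that at least one of six estimates reaches 0.25, at r = 0.6, with Digit Coding signed correctly and then reversed, under a uniform true benefit of 0.25:

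| ρ | Correct | Reversed |
|---|---|---|
| 0 | 98.4% | 96.9% |
| 0.3 | 91.9% | 89.6% |
| 0.5 | 85.7% | 83.4% |
| 0.7 | 77.7% | 75.7% |

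Change over r of 0.6 to 0.9 and ρ of 0 to 0.7:

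- uniform benefit 0.25: falls by 1.6 to 2.4 percentage points
- uniform benefit 0.10: falls by 0.8 to 6.3 points
- no effect: rises by 0 to 3.7 points
- benefit of 0.25 in Digit Coding alone: falls by 36 to 50 points

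Telephone Search does not enter this rule.

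**3. Is there evidence that a wrong sign was used?**

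*Composite.* In Table 14.2 the Cognition coefficients are −0.14 for hearing and −15.45 for visual acuity. On both covariates a higher value is worse (note to Table 14.1). Section 14 says that poorer hearing or vision went with worse performance, and the Table 14.2 note marks only ATTR and Timed IADL as lower-is-better. The reported Cognition composite therefore runs higher-is-better.

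*Items.* Section 14 puts Trails A and B, Digit Coding, and the TEA visual elevator and telephone search subtests in that composite. The unweighted mean of the five item d values in Table 14.3 is a rough guide to the sign of the composite d. For the overall column: (0.03 − 0.17 + 0.08 + 0.02 − 0.29)/5 = −0.066. The same sum for each column:

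| Column | Composite d | As printed | Digit Coding flipped | Telephone Search flipped | Both flipped |
|---|---|---|---|---|---|
| Overall | −0.03 | −0.066 | −0.098 | +0.050 | +0.018 |
| Adherent | −0.03 | −0.070 | −0.106 | +0.058 | +0.022 |
| Non-MCI | −0.10 | +0.036 | +0.012 | +0.004 | −0.020 |
| MCI | +0.08 | +0.064 | −0.040 | +0.172 | +0.068 |

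The printed signs agree with the composite's sign in three of four columns. The alternatives agree in two, one and two. No combination reproduces the size of the non-MCI value.

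**The case against.** The strongest reply is that this is a slip in a measure description and that the analysts knew the right direction. Much of that stands. The Table 14.3 note fixes a sign convention that covers single items. Trails A is a completion time, yet its +0.43 in MCI is reported as improvement, so items were evidently oriented one by one. Aim 1 tests composites, not items, and the item effect sizes are descriptive. Section 9.5 frames the interim criterion as improvement. The interim figures above also need an analyst who followed a sentence that ranks zero correct above a perfect score.

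Two stronger readings are tempting, and the documents support neither. A reader might infer that the MCI result for Digit Coding (+0.26) is really a harm. The sign note and the three-column agreement count against that, though they do not prove each sign. A reader might also use the overall Telephone Search effect of −0.29, the largest absolute value in its column, to size the problem. That cell fits badly with its own row: the subgroup values weighted by n give (146 × 0.08 + 52 × (−0.27))/198 = −0.01. Different subgroup SDs may contribute, so this is no proof of a sign error, but it makes the cell unsuitable as a yardstick.

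What the reply does not remove is the text itself. The signs used at interim are not reported, and Section 13 offers the data for re-use, so others will depend on these definitions.

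**Conclusion.** Wrong as written, with minor consequence. Both contradictions stand in complete sentences and need no outside source. Followed literally, the Digit Coding sentence would reverse that measure's sign in the interim rule and in the item-level effect sizes. The cost at interim is about 2 percentage points under a uniform benefit of 0.25, and it becomes large (36 to 50 points) only if the benefit lies in Digit Coding alone. These figures rest on 70 per arm, the assumed correlations and true effects, and the written direction having been applied. Nothing in the documents shows that it was, and the composite and most of Table 14.3 suggest that it was not. The item check is supportive rather than conclusive, because the non-MCI column does not fit.

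**What to change.** In Section 6.3.5, state that higher Digit Symbol Coding scores are better. Make the Telephone Search label and formula agree with the score actually recorded, and give its direction; Table 14.3 names the row as a time, which suggests time divided by targets with lower better, but the sponsor must confirm this. Then confirm from the scoring code the sign used for Digit Coding at the interim analysis and for both measures in Table 14.3, and look at the overall Telephone Search cell in the same pass. The cost is two corrected sentences and a sign check of two items. No reanalysis is needed unless the check finds a wrong sign.
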